10.1.1.2 Analysis of PASI score and response

Summaries of the PASI75, PASI90 and PASI100 response will be summarized descriptively using counts and percentages by PS0010/PS0011 treatment group and visit. In general, summaries of PASI score and response will include only PS0011 visits. PS0010 visits will be added for select summaries as specified.

The PASI responder variables will be derived relative to both the PS0010 Baseline and the PS0011 Baseline for subjects who are PS0010 Week 12 PASI90 non-responders at PS0010 Week 12 in the following treatment groups: Placebo to BKZ 160mg, BKZ 64mg to BKZ 160mg, BKZ 160mg to BKZ 320mg, BKZ 320mg to BKZ 320mg, and BKZ 480mg to BKZ 320mg. PASI response will be calculated relative to the original PS0010 Baseline only for subjects who are PS0010 Week 12 PASI90 responders in the following treatment groups: Placebo to Placebo, BKZ 64mg to BKZ 64mg, BKZ 160mg to BKZ 160mg, BKZ 320mg to BKZ 320mg, and BKZ 480mg to BKZ 320mg. Missing data will be imputed via NRI. Summaries for PASI90 and PASI100 response will include PS0010 visits.

In addition, PASI90 and PASI100 response relative to the PS0010 Baseline will also be summarized descriptively using counts and percentages by PS0011 treatment group and visit. Missing data will be imputed via NRI.

Change from Baseline in PASI score will be summarized using descriptive statistics by PS0010/PS0011 treatment group and visit separately by PS0010 Week 12 PASI90 response. The table will display descriptive statistics for the PS0010 Baseline, followed by descriptive statistics for the change from PS0010 Baseline for all treatment groups. The change from PS0011 Baseline will also be displayed for subjects who are PS0010 Week 12 PASI90 non-responders at PS0010 Week 12 in the following treatment groups: Placebo to BKZ 160mg, BKZ 64mg to BKZ 160mg, BKZ 160mg to BKZ 320mg, BKZ 320mg to BKZ 320mg, and BKZ 480mg to BKZ 320mg. A similar summary will be presented for the percent change from Baseline in PASI score.

Missing data for the continuous change from Baseline and percent change from Baseline variables will be handled by using MI via the MCMC method specified in Section 4.2.2. Supportive summaries will be based on observed data.

In addition, the percent change from PS0010 Baseline in PASI score will also be presented using descriptive statistics by PS0011 treatment group and visit. Missing data will be handled using the same multiple imputation as described above.

A line plot of the mean percentage change from PS0010 Baseline in PASI score over time using MI via the MCMC method specified in Section 4.2.2, by PS0010/PS0011 treatment group will be produced.

The number and percentage of subjects who achieve an absolute PASI score ≤ 1 , ≤ 2 , ≤ 3 , and ≤ 5 at each visit will be summarized by both PS0010/PS0011 treatment group and PS0011 treatment group. Missing data will be imputed using NRI. These summaries will include PS0010 visits.

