4.4.1 Secondary efficacy variables

The secondary efficacy variables are:

- PASI90 response over time
- IGA response (Clear or Almost Clear with at least a 2 category improvement from Baseline on a 5-point scale) over time

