5 STUDY DESIGN

5.1 Study description

PS0011 is a multicenter, 48-week, double-blind, placebo-controlled, parallel-group, extension study to assess the long-term safety, tolerability, and efficacy of bimekizumab in eligible adult subjects with moderate to severe chronic plaque psoriasis who complete PS0010. At Week 12 of PS0010, all eligible subjects continuing into PS0011 will undergo the PS0010 Week 12 study assessments and any additional PS0011 Baseline assessments, and will then receive their first dose of bimekizumab or placebo in PS0011.

During the Treatment Period, subjects will attend study visits at the study site Q4W for study assessments and administration of bimekizumab or placebo by study site staff through Week 48. Any subject who does not achieve PASI75 response at Week 12 or later in PS0011 will be withdrawn from study treatment and will return to complete the Early Withdrawal Visit assessments. Following completion or early withdrawal from the 48-week Treatment Period, subjects will return for a SFU Visit 20 weeks after their last dose of bimekizumab or placebo in PS0011.

Subjects withdrawing early from the study will undergo the Early Withdrawal Visit assessments and will enter the SFU Period.

Subjects who received placebo or bimekizumab 64mg, 160mg, or 320mg loading dose + 160mg Q4W in PS0010 must achieve PASI90 response at Week 12 in PS0010 to enter the PS0011 extension study on the same treatment dose. Subjects who do not achieve PASI90 response at Week 12 in PS0010 while receiving placebo or bimekizumab 64mg Q4W will be assigned to receive bimekizumab 160mg Q4W on entering PS0011. Subjects who do not achieve PASI90 response at Week 12 in PS0010 while receiving bimekizumab 160mg or 320mg loading dose + 160mg Q4W will be assigned to receive bimekizumab 320mg Q4W on entering PS0011. Subjects who receive bimekizumab 320mg or 480mg Q4W in PS0010 will be assigned to receive bimekizumab 320mg Q4W on entering PS0011, regardless of their PASI90 response at Week 12 in PS0010.

A schedule of study assessments is presented in [Table 5–1](#).

A study schematic diagram of PS0011 is presented in [Figure 5–1](#).

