5.4 Rationale for study design and selection of dose

PS0011 is a 48-week, double-blind, placebo-controlled, parallel-group extension study for eligible subjects who complete PS0010, a Phase 2b, randomized, double-blind, placebo-controlled, parallel-group, dose-ranging study in adult subjects with moderate to severe chronic plaque psoriasis. Because some PS0010 subjects may have severe disease, the treatment in PS0011 provides more time to respond to a potentially efficacious treatment. PS0011 also provides an opportunity for nonresponding PS0010 placebo subjects to receive bimekizumab. This study will allow the collection of further data on the long-term safety, tolerability, and efficacy of bimekizumab in this subject population.

The PS0011 design (Figure 5–1) allows PASI90 responders in PS0010 to continue their dose in PS0011, thus permitting these subjects to remain on the dose that resulted in this response after 12 weeks of initial treatment in PS0010. It also provides an opportunity for an increased dose among PS0010 nonresponders (ie, <PASI90). PASI90 was selected as the response criterion in PS0010 to ensure that a sufficiently high efficacy response was achieved. This type of dose escalation for those who do not achieve a desired response after 12 weeks is common in clinical practice.

Regardless of PASI90 response at Week 12 of PS0010, subjects who received the 2 highest doses of bimekizumab (320mg and 480mg Q4W) in PS0010 will begin PS0011 on the 320mg Q4W dose. For those subjects who do achieve PASI90 response, this will allow a continuation of the PS0010 dose for subjects initially receiving 320mg Q4W and a dose down for subjects originally randomized to the 480mg Q4W dose. Because bimekizumab 480mg Q4W is the highest dose evaluated in PS0010 and because it requires 3 injections, it will be of interest to evaluate whether these subjects can maintain response in PS0011 with the lower 320mg dose, allowing the blind to be maintained with the use of only 2 injections at each study administration visit.

To protect against the possibility of exposing subjects to an ineffective treatment for extended periods of time, subjects across all treatment groups who have not achieved PASI75 response at Week 12 or later in PS0011 will be withdrawn from study treatment. Because this withdrawal decision is based strictly on the PASI response and not on the original study treatment, it can be done in such a way that will not unblind subjects or Investigators.

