14.6 Planned efficacy analyses

Efficacy variables will be summarized based on the FAS. The summaries described in this section will provide data on maintenance of effect of study treatment over 48 weeks.

Responder efficacy variables (PASI75, PASI90, PASI100, IGA, and DLQI score of 0 or 1) will be summarized descriptively using counts and percentages by scheduled visit and PS0010/PS0011 treatment group. The PASI responder variables will be derived relative to both the PS0010 Baseline and the PS0011 Baseline with responder rates being presented side-by-side in applicable summary tables. Missing data will be handled by using nonresponder imputation (NRI), meaning that subjects that discontinue early or who have missing data at a given time point are imputed as though they did not achieve the given response. Supportive summaries will be based on observed case data.

Continuous efficacy variables based on the change from Baseline (PASI, DLQI, BSA, mNAPSI, PSSI, PGADA, SF-36, and HADS) will be summarized using descriptive statistics by scheduled visit and PS0010/PS0011 treatment group. The table presentations will display descriptive statistics for the PS0010 Baseline, followed by descriptive statistics for the observed, change from PS0010 Baseline, and change from PS0011 Baseline results by scheduled visit for PS0011. Figures for selected variables will also be generated in order to demonstrate the kinetics of response over time. Missing data will be handled by using multiple imputation (MI) via the Markov-Chain Monte Carlo (MCMC) method. Supportive summaries will be based on observed case data.

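### In the 64mg, 160mg and loading-dose arms, one Week 12 PASI90 reading sets the PS0011 path and also defines the table rows, so part of any later PASI90 rise or fall is regression to the mean, and no planned table rejoins the arms

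*SAP*

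**What the plan says.** Protocol 5.1 sets the PS0011 dose from one reading in four of the six PS0010 arms. Subjects on placebo, 64mg, 160mg or 320mg loading + 160mg "must achieve PASI90 response at Week 12 in PS0010 to enter the PS0011 extension study on the same treatment dose". Those below the threshold move up: "Subjects who do not achieve PASI90 response at Week 12 in PS0010 while receiving placebo or bimekizumab 64mg Q4W will be assigned to receive" 160mg Q4W, and those from the two 160mg arms go to 320mg Q4W. No second reading is involved. Subjects from the 320mg and 480mg arms all receive 320mg Q4W "regardless of their PASI90 response at Week 12 in PS0010".

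The same threshold then returns as an outcome. Protocol 4.4.1 lists "PASI90 response over time" as a secondary efficacy variable, and SAP 10.1.1.1 uses the same 90% cut. SAP 10.1.1.2 gives the layout: "Summaries of the PASI75, PASI90 and PASI100 response will be summarized descriptively using counts and percentages by PS0010/PS0011 treatment group and visit". SAP 10.1 further splits efficacy tables by PS0010 Week 12 PASI90 status unless otherwise specified, and SAP 10.1.1.2 includes PS0010 visits in the PASI90 and PASI100 tables. Missing values are counted as non-response (SAP 4.2.2), and subjects below PASI75 at PS0011 Week 12 or later are withdrawn from treatment (Protocol 5.1).

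On purpose, Protocol 14.6 says: "The summaries described in this section will provide data on maintenance of effect of study treatment over 48 weeks".

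**The concern.** When a group is selected because a noisy reading fell on one side of a cut, the next reading on the same cut drifts back even if nothing has changed. Here the selecting visit appears in the same table as the outcome, so the reader sees 0% rising after a dose increase and 100% falling on an unchanged dose. The first looks like benefit from escalation and the second like loss of maintenance. Part of each comes from the sorting alone.

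The selection cancels only when both halves of an arm are read together. For the 64mg and 160mg arms the SAP offers the PS0010/PS0011 path or the PS0011 treatment group. The latter does not help. The PS0011 64mg column holds only selected responders, and the 160mg column mixes placebo and 64mg non-responders with responders from the 160mg arms. SAP 10.1.1.2 also shows non-responders against the PS0011 Baseline, which is normally the selecting reading itself.

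**Working it through.** **Plan's own figure.** There is none to reproduce. Enrolment of up to 240 is carried over from PS0010 (Protocol 14.8), and neither document gives a PASI90 rate or a PASI repeatability.

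**Model.** Each log residual PASI is a stable true level plus independent visit noise, with no dose or time effect. Let p be the PASI90 rate, rho the between-visit correlation, and p11 the probability of PASI90 at both visits (bivariate normal). Then:

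- false gain among Week 12 non-responders = (p − p11)/(1 − p)
- false loss among Week 12 responders = (p − p11)/p

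**Assumed inputs.** Between-subject SD 0.8 to 1.2, visit-to-visit SD 0.2 to 0.4, p = 0.40 to 0.75. With rho = between-variance/(between-variance + visit-variance), this spans 0.64/(0.64 + 0.16) = 0.80 to 1.44/(1.44 + 0.04) = 0.97.

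**Worked case, p = 0.60 and rho = 0.80.** p11 = 0.501. Gain = (0.600 − 0.501)/0.40 = 24.8%. Loss = (0.600 − 0.501)/0.60 = 16.5%. If the six arms are equal, 240/6 = 40 per arm, so there are 24 responders and 16 non-responders. About 0.248 × 16 = 4 gain and 0.165 × 24 = 4 lose. The pooled rate is (24 − 4 + 4)/40 = 60%, unchanged.

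**Single later visit, across the assumptions.**

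| Between SD, visit SD | p | Gain | Loss |
|---|---|---|---|
| 1.2, 0.2 | 0.40 | 6.0% | 9.0% |
| 0.8, 0.2 | 0.60 | 13.3% | 8.9% |
| 0.8, 0.3 | 0.60 | 19.3% | 12.9% |
| 0.8, 0.4 | 0.60 | 24.8% | 16.5% |
| 0.8, 0.4 | 0.75 | 32.4% | 10.8% |
| 0.8, 0.4 | 0.40 | 16.5% | 24.8% |
| 1.2, 0.2 | 0.75 | 11.8% | 3.9% |

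Gain therefore runs from 6% to 32% and loss from 4% to 25%. With rho widened to 0.70 to 0.95, gain is 8% to 40% and loss 5% to 31%. Even at rho = 0.99 the gain is 3.6% to 7.2%.

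**Adding the plan's own rules.** Simulation of 400,000 subjects per setting, with withdrawal below PASI75 at each visit from Week 12 to Week 48, then non-responder imputation:

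- Week 48 gain is 6% to 28% overall, and 13% to 20% for between-subject SD 0.8 and p = 0.60.
- The pooled rate no longer stays put. It falls by 0 to 3 points under the assumptions above (for example 60% to 57.5%).
- Under wider assumptions (log SD 1.0 or 1.4), p = 0.60 and rho = 0.80 give a pooled Week 48 rate of 51.9% to 56.2%, a fall of about 4 to 8 points. At rho = 0.70 the fall reaches about 14 points (for example 40% to 25.8%).
- In observed-case tables from the wider simulation, the non-responder rate at Week 48 is 21% to 71%, because the withdrawal rule leaves the better subjects.

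**Placebo-to-160mg.** With an assumed placebo PASI90 rate of 2% to 5% and rho 0.70 to 0.95, the gain is 0.6% to 3.2%.

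**The case against.** The plan never draws the inference. Protocol 14.2 rules out inferential analyses, the primary objective is safety, and no text attributes a rise after escalation to dose. Following Week 12 responders is a natural descriptive display of maintenance. This stands, and it limits the point to presentation.

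A no-dose-change comparison is already in the tables. Under the SAP 10.1 split, 320mg-to-320mg non-responders appear beside the escalated groups, and any rise in their row is noise plus time without a dose change. This also stands in part. Neither document designates that row as a reference, Protocol 14.2 does not separate responders within that group, and it is inexact: at rho = 0.80 the no-effect gain is 32.4% if that arm's rate is 75%, against 24.8% for an arm at 60%.

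A reader could add the counts from the two path rows by hand, since both use the PS0010 Baseline and the same imputation. That is true. It shows how little the added table costs, but the SAP does not prompt anyone to do it.

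The size is wholly assumed, and the model has no mass at PASI 0, so stable, fully clear subjects are not represented. The direction of the artefact does not depend on this; the size does.

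A pooled row is not a clean remedy either. It mixes two doses, leaves out subjects who did not enter PS0011, and cannot separate time or the as-needed topicals allowed by Protocol 7.8.1.

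**Conclusion.** The point holds for the 64mg, 160mg and 320mg loading + 160mg arms. The rows begin at 0% and 100% by construction, so for any repeatability below 1 part of the later movement is regression to the mean. The size, about 6% to 32% gain and 4% to 25% loss at one later visit, rests on assumed repeatability and response rates and on no dose or time effect.

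Three stronger readings are tempting and not supported. A reader might infer that all dose-escalation groups are affected alike; in placebo-to-160mg the artefact is about 1% to 3%, so a large rise there would not be explained by it. A reader might infer that observed rises are mostly spurious; real improvement with dose or time is possible, and Protocol 5.4 expects some subjects to need longer to respond. A reader might infer that pooling gives an undistorted rate; it removes the selection effect but keeps the downward drift from PASI75 withdrawal with non-responder imputation. Since nothing is tested, this is a minor point.

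**What to change.** In SAP 10.1.1.2 and 10.1.2.2, add one supportive table each for PASI90, PASI100 and IGA response, relative to PS0010 Baseline, with non-responder imputation and both PS0010 and PS0011 visits. Present it by PS0010 arm among subjects entering PS0011, pooling both paths: 64-to-64 with 64-to-160, and 160-to-160 with 160-to-320 (with and without the loading dose).

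Footnote the path-specific tables: changes from 0% or 100% at PS0010 Week 12 include regression to the mean, and 320mg-to-320mg by responder status is an inexact no-dose-change reference.

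Footnote the pooled table: it mixes doses, covers only subjects who entered PS0011, and still carries the drift from PASI75 withdrawal with non-responder imputation.

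A row requiring the change at two consecutive visits is optional. It lowers the false gain to about 3% to 19% but does not remove it.

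The cost is one extra table per responder variable from data already held. Treatment assignment, assessments and existing tables stay as they are.

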10.1.2 IGA response

10.1.2.1 Derivation of IGA response

A static IGA for psoriasis will be used to assess disease severity in all subjects during the study.

The Investigator will assess the overall severity of psoriasis using the following five-point scale (see [Table 10-1](#)):

Table 10–1: Five-point Investigator's Global Assessment

Score	Short Descriptor	Detailed Descriptor
0	Clear	No signs of psoriasis; post-inflammatory hyperpigmentation may be present
1	Almost clear	No thickening; normal to pink coloration; no to minimal focal scaling
2	Mild	Just detectable to mild thickening; pink to light red coloration; predominately fine scaling
3	Moderate	Clearly distinguishable to moderate thickening; dull to bright red, clearly distinguishable to moderate thickening; moderate scaling
4	Severe	Severe thickening with hard edges; bright to deep dark red coloration; severe/coarse scaling covering almost all or all lesions

IGA response is defined as clear (0) or almost clear (1) with at least a two category improvement from Baseline.

10.1.2.2 Analysis of IGA response

The number and percentage of subjects achieving an IGA response (defined as clear (0) or almost clear (1) with at least two category improvement from Baseline) will be summarized descriptively using counts and percentages by PS0010/PS0011 treatment group and visit. In general, summaries of PASI score and response will include only PS0011 visits. PS0010 visits will be added for select summaries as specified.

The IGA response variables will be derived relative to both the PS0010 Baseline and the PS0011 Baseline for subjects who are PS0010 Week 12 PASI90 non-responders in the following treatment groups: Placebo to BKZ 160mg, BKZ 64mg to BKZ 160mg, BKZ 160mg to BKZ 320mg, BKZ 320mg to BKZ 320mg, and BKZ 480 mg to BKZ 320mg. PASI response will be calculated relative to the original PS0010 Baseline only for subjects who are PS0010 Week 12 PASI90 responders in the following treatment groups: Placebo to Placebo, BKZ 64mg Q4W to

BKZ 64mg Q4W, BKZ 160mg Q4W to BKZ 160mg Q4W, BKZ 320mg Q4W to BKZ 320mg Q4W, and BKZ 480mg Q4W to BKZ 320mg Q4W. Missing data will be imputed via NRI. Summaries for IGA response will include PS0010 visits.

IGA response relative to the PS0010 Baseline will also be summarized descriptively using counts and percentages by PS0011 treatment group and visit. Missing data will be imputed via NRI.

In addition, a shift table of IGA response compared to PS0010 Baseline will be summarized by PS0010/PS0011 treatment group based on observed data.

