2.2.4 Efficacy variables

Change from Baseline and responder variables will be defined relative to the PS0010 Baseline for subjects who are PS0010 Week 12 PASI90 responders and relative to both the PS0010 and PS0011 Baselines for subjects who are PS0010 Week 12 PASI90 non-responders).

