2.2.4.1 Secondary efficacy variables

The secondary efficacy variables are:

- Psoriasis Area and Severity Index (PASI)90 response (defined as a subject that achieves 90% reduction in the PASI score from the Baseline of PS0010) over time
- Investigator's Global Assessment (IGA) response (Clear or Almost Clear with at least a 2 category improvement from Baseline on a 5-point scale) over time

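### IGA response measured from the PS0011 Baseline cannot be met from IGA 1 and needs full clearance from IGA 2, yet those subjects stay in the denominator

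*SAP*

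**What the plan says.** IGA response over time is one of two secondary efficacy variables. SAP 2.2.4.1 describes it as IGA "response (Clear or Almost Clear with at least a 2 category improvement from Baseline on a 5-point scale) over time" and does not name the Baseline, whereas the line above it ties PASI90 to the PS0010 Baseline. The derivation in SAP 10.1.2.1 is: "IGA response is defined as clear (0) or almost clear (1) with at least a two category improvement from Baseline".

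SAP 2.2.4 sets a general rule. Responder variables use the PS0010 Baseline for PS0010 Week 12 PASI90 responders, and are defined "relative to both the PS0010 and PS0011 Baselines for subjects who are PS0010 Week 12 PASI90 non-responders". SAP 10.1.2.2 applies this to IGA: "The IGA response variables will be derived relative to both the PS0010 Baseline and the PS0011 Baseline for subjects who are PS0010 Week 12"; the rest of the sentence confines it to those who missed PASI90. The groups are "Placebo to BKZ 160mg, BKZ 64mg to BKZ 160mg, BKZ 160mg to BKZ 320mg, BKZ 320mg to BKZ 320mg", together with 480 mg to 320 mg. The matching sentence for PASI90 responders reads "PASI response will be calculated relative to the original PS0010 Baseline only for subjects who are PS0010 Week 12 PASI90 responders", although it stands in the IGA section.

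Other provisions that bear on the point:
- SAP 10.1.2.2 also reports IGA response from the PS0010 Baseline by PS0011 treatment group, includes PS0010 visits in the IGA summaries, and plans a shift table from the PS0010 Baseline. SAP 2.2.4.2 lists the IGA shift from the PS0011 Baseline.
- SAP 4.2.2 counts missing data and early discontinuation as non-response. No rule covers subjects who cannot meet the definition.
- Protocol 14.6 asks for both Baselines only for the PASI responder variables. Protocol 14.2 plans no inferential analysis.

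**The concern.** Re-basing works for a percentage criterion such as PASI90, because any starting PASI above zero leaves room for a 90% fall. It does not carry over to a fixed two-category gain on a five-point scale, which the better starting scores cannot deliver. A subject who enters PS0011 almost clear and becomes fully clear is an IGA non-responder from the PS0011 Baseline at every visit.

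The rule applies to PASI90 non-responders after 12 weeks in PS0010. Those who had active drug may include near-misses at IGA 1 or 2; those who had placebo are less likely to. The shortfall then differs between groups shown in the same table, for a secondary variable, and nothing in the table warns the reader.

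**Working it through.** The plan gives no figure on this point, so there is none to reproduce. The check has four steps.

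**1. Which scores qualify.** A post-Baseline score p counts if p is 0 or 1 and b − p is at least 2, where b is the Baseline IGA (SAP 10.1.2.1).

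| Baseline IGA (b) | Scores that count as response |
|---|---|
| 0 | none |
| 1 | none |
| 2 | 0 only |
| 3 | 0 or 1 |
| 4 | 0 or 1 |

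This is exact and needs no assumption.

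**2. Whether the blocked scores can occur among PASI90 non-responders.**
- IGA 0 means no signs of psoriasis, so PASI is 0, the improvement is 100%, and the subject is a PASI90 responder. This cell should be empty.
- IGA 1 excludes thickening but allows pink colour and minimal focal scaling. In the PASI formula of SAP 10.1.1.1, take redness 1, thickness 0, scaling 1 and area grade 2 in all four regions. PASI = (0.1 + 0.2 + 0.3 + 0.4) × (1 + 0 + 1) × 2 = 4.0. For assumed PS0010 Baseline PASI values of 12, 15, 20 and 30, the improvement is 100 × (base − 4.0)/base = 66.7%, 73.3%, 80.0% and 86.7%. All are below 90%.
- With redness alone, PASI = 1.0 × 1 × 2 = 2.0, which is (15 − 2)/15 = 86.7% from an assumed 15. So IGA 1 can coexist with PASI90 non-response.

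**3. What happens to such a subject.** If PASI falls from 4.0 to 0 during PS0011, the improvement from the PS0011 Baseline is 100%, so PASI75, PASI90 and PASI100 are all met (SAP 10.1.1). At the same visit and from the same Baseline, IGA response is not met, because 1 − 0 = 1 is less than 2.

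**4. Size.** Let p1 be the share of a group's non-responders at PS0011 Baseline IGA 1. The ceiling is 1 − p1.

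| Assumed p1 | 0% | 10% | 20% | 30% | 40% | 50% |
|---|---|---|---|---|---|---|
| Ceiling | 100% | 90% | 80% | 70% | 60% | 50% |

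IGA 2 adds a shortfall without an absolute cap. As an illustration with every input assumed, let 85% of those starting at IGA 3–4, 90% of those at IGA 2 and 95% of those at IGA 1 be at IGA 0/1 later, let a fraction c of the IGA 2 starters reach IGA 0, and let all have a PS0010 Baseline IGA of at least 3.
- p1 = 0, p2 = 0.2, c = 0.7. From the PS0011 Baseline: 0.8 × 0.85 + 0.2 × 0.7 = 82%. From the PS0010 Baseline: 0.8 × 0.85 + 0.2 × 0.90 = 86%.
- p1 = 0.2, p2 = 0.4, c = 0.4. From the PS0011 Baseline: 0.4 × 0.85 + 0.4 × 0.4 = 50%. From the PS0010 Baseline: 0.4 × 0.85 + 0.4 × 0.90 + 0.2 × 0.95 = 89%.

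The spread shows how far the result depends on the starting scores. It is not an estimate for this trial.

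**The case against.** The best defence is that the unaffected rate is already planned. The same subjects have an IGA response from the PS0010 Baseline, and the summary by PS0011 treatment group uses only that version. That stands, and it limits the harm to how one column is read. The PS0010-Baseline rate is fully attainable only if PS0010 Baseline IGA was at least 3, which these documents do not state.

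The starting position is also partly visible. IGA summaries include PS0010 visits, efficacy tables are split by PASI90 status (SAP 10.1), and PS0011 Baseline assessments are those of PS0010 Week 12 (Protocol Table 5-1, note f). On the same assumption about entry IGA, the Week 12 rate in non-responders shows who starts at IGA 1. This stands in part: it does not show who starts at IGA 2, and the reader must make the link.

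No decision depends on the rate. PS0011 treatment is not randomized (Protocol 7.10), nothing is tested, and groups defined by earlier treatment and response are confounded in any case. That is correct and keeps the point modest, but it does not make the column right.

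Four stronger readings are tempting and are not supported:
- A reader might infer a bias against switching from active drug. But 320-320 is not a switch and is affected, while placebo-160 is a switch and probably affected little. No section says the column isolates what a new dose adds; Protocol 14.6 speaks of maintenance of effect.
- A reader might infer a built-in gap of 5 to 40 points between groups. That only restates assumed shares: 10–40% at IGA 1 in active groups gives ceilings of 60–90%, and 0–5% in placebo gives 95–100%.
- A reader might infer that PASI90 responders have no Baseline rule for IGA. SAP 2.2.4 supplies it; the reference to PASI is a wording slip.
- A reader might treat IGA 2 as capped too. It is a stricter target, and it can be met.

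**Conclusion.** The point holds in limited form. The definition and the re-basing are both explicit in the SAP, and together they make response from the PS0011 Baseline impossible from IGA 1. The understatement follows wherever non-responders start PS0011 at IGA 1, or start at IGA 2 and reach only IGA 1. That it is larger in the groups treated with active drug in PS0010 is likely but is not shown by the documents. Its size cannot be derived from them, and the ceiling disappears if no non-responder starts at IGA 1. It affects the interpretation of a descriptive secondary rate, with no effect on error rates, power or the primary safety objective.

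**What to change.** Choose one of two changes in SAP 10.1.2.2:
- Drop the PS0011-Baseline version of IGA response and rely on the PS0010 Baseline. SAP 2.2.4 then needs an exception for IGA, and SAP 2.2.4.1 should name the PS0010 Baseline, as it does for PASI90. This is compatible with Protocol 14.6.
- Or keep it, with the denominator limited to subjects who can meet the definition (PS0011 Baseline IGA 2 or higher), shown separately for IGA 2 and for IGA 3 or higher, with n in each.

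In either case, provide the IGA shift table from the PS0011 Baseline that SAP 2.2.4.2 lists, and replace PASI with IGA in the sentence on PASI90 responders.

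The cost is a sentence or two, a filter and one table. The restricted version has fewer subjects: 240 spread evenly over six feeder regimens is 240/6 = 40 per regimen before any split by response. It also selects on Week 12 status, so it makes the rate meaningful within a group but does not make the groups comparable. Dropping the version avoids both drawbacks.
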